11.1.5.6. Vital Signs

All vital signs (body temperature, heart rate, respiratory rate, systolic blood pressure, diastolic blood pressure) will be presented by treatment group using descriptive statistics.

The analyses will be done for the vital signs assessments at baseline, at the first 7 daily assessments as well as for the pre-post differences of the daily vital signs assessments described in Section 10.3.4.4 separately.

Note: Vital sign assessments will only be recorded while a subject is hospitalized. It may however be the case that certain subjects will be discharged during the first week, making some of the measurements not available. The respective subjects will be excluded from all vital sign analysis referring to time points after hospital discharge.

Furthermore, for the vital signs assessment at baseline and at the first 7 daily assessments the information whether the overall vital signs investigator's assessment was normal, abnormal (NCS) or abnormal (CS) is given in the eCRF. For these overall vital signs investigator's assessment classifications, a shift table will be produced indicating shifts from baseline to each of the daily assessments from day 1 to day 7 and to the last daily assessment within the first 7 days.

Additionally, for individual vital signs parameters a shift table will be produced indicating shifts from baseline to post treatment potentially clinically significant (pCS) results at each of the daily assessments from day 1 to day 7 and at the last daily assessment within the first 7 days.

Furthermore, a shift table indicating shifts from baseline to any post treatment potentially clinically significant result within the first 7 daily assessments will be provided. A subject listing of patients experiencing such shifts will be provided. As additional analysis, this shift analysis will be repeated excluding subjects with hospital discharge before day 7.

11.1.5.7. Pain Assessment

The pain assessment score (FPS-R) will be analyzed descriptively by treatment group with counts and percentages and compared between groups using a chi square test (or Fisher's exact test in case of small estimated cell counts). Additionally, the pain score will be evaluated as a metric variable and presented using numeric descriptive statistics by treatment group.

The analyses will be done for the pain assessments at screening, pre and post eschar removal procedures as well as at the first 7 daily assessments separately. Changes from baseline per time point as calculated in Section 10.3.4.4, will be presented by treatment group using descriptive statistics.

Note: Pain assessments will only be recorded while a subject is hospitalized. It may however be the case that certain subjects will be discharged during the first week, making some of the measurements not available. The respective subjects will be excluded from all pain analysis referring to time points after hospital discharge.

Furthermore, for the pain assessment at screening, pre and post eschar removal procedures and at the first 7 daily assessments the information whether the pain assessment was normal, abnormal (NCS) or abnormal (CS) is given in the eCRF. These classifications will be analyzed separately for each time point of pain assessment by displaying shifts from baseline by treatment group.

Furthermore, a shift table indicating shifts from baseline to any abnormal (NCS) or any abnormal (CS) result will be provided. As additional analysis, this shift analysis will be repeated excluding subjects with hospital discharge before day 7.

The Pain scale (FPS-R) was validated only for children above the age of 4. The analyses described above will be therefore done for the children above the age of 4 and below the age of 4 separately.

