11.1.5.13. Hospital Readmission Rates

Hospital admission rates will be analyzed on a patient level by displaying counts and percentages by treatment group. The proportion of patients needing readmission to a hospital will be compared between treatment groups using a chi square test (or Fisher's exact test in case of small estimated cell counts).

Furthermore, the number of planned hospital readmissions per patient will be analyzed by displaying counts and percentages by treatment group. The number of planned hospital readmissions per patient will be compared between treatment groups using a chi square test (or Fisher's exact test in case of small estimated cell counts).

Additionally, the number of unplanned hospital readmissions per patient will be analyzed by displaying counts and percentages by treatment group. The number of unplanned hospital readmissions per patient will be compared between treatment groups using a chi square test (or Fisher's exact test in case of small estimated cell counts).

Hospital readmission will also be analyzed on a readmission level. Counts and percentages of planned/unplanned readmissions will be displayed by treatment group. The proportion of planned/unplanned readmissions to hospitals will be compared between treatment groups using a chi square test (or Fisher's exact test in case of small estimated cell counts).

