11.1.6.4. Incidence of surgically harvested donor site wounds

This is a counting variable, giving the number of donor site wounds per patient. Rates of patients with different numbers of donor site wounds will be analyzed by displaying counts and percentages by treatment group. The number of donor site wounds will be compared between treatment groups using a chi square test (or Fisher's exact test in case of small estimated cell counts).

11.1.6.5. % area of surgically harvested donor site wounds

The % wound area of surgically harvested donor site wounds per patient (computed as in section 10.3.5.5) will be presented by treatment group using descriptive statistics and compared between groups with a one-way analysis of variance.

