11.1.9. Handling of Multiple Comparisons

Unless otherwise specified, all statistical tests will be conducted against a two-sided alternative hypothesis, employing a significance level of 0.05. The primary and secondary endpoints of efficacy will be tested in a hierarchy, so as to preserve the nominal significance levels:

- 1. Primary: time to complete eschar removal
- 2. Secondary: Incidence of surgical excision
- 3. Secondary: Blood loss
- 4. Secondary: Area of Autograft in DPT wounds

5. Secondary: Incidence of Autograft in DPT wounds

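### FPS-R pain score and donor-site number (and, as a lesser point, readmission counts) are ordered outcomes tested only by a chi-square/Fisher test that ignores the order

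*SAP*

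**What the plan says.** **Pain.** SAP 11.1.5.7: "The pain assessment score (FPS-R) will be analyzed descriptively by treatment group with counts and percentages and compared between groups using a chi square test"; when estimated cell counts are small, the fallback is Fisher's exact test. This is done at screening, before and after eschar removal procedures, and at the first seven daily assessments. The numeric version carries no test: "Additionally, the pain score will be evaluated as a metric variable and presented using numeric descriptive statistics by treatment group". Nor do the changes: "Changes from baseline per time point as calculated in Section 10.3.4.4, will be presented by treatment group using descriptive statistics". Because FPS-R was validated only above age 4, "The analyses described above will be therefore done for the children above the age of 4 and below the age of 4 separately".

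**Donor sites.** SAP 11.1.6.4 calls the number per patient a counting variable, then says "The number of donor site wounds will be compared between treatment groups using a chi square test", again with the Fisher fallback. The area harvested is a separate endpoint, compared by one-way ANOVA (11.1.6.5).

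**Readmissions.** SAP 11.1.5.13 first compares the proportion of patients with any readmission. It then adds "The number of planned hospital readmissions per patient will be compared between treatment groups using a chi square test" and "The number of unplanned hospital readmissions per patient will be compared between treatment groups using a chi square test", both with the Fisher fallback.

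**Level and scope.** SAP 11.1.9: "all statistical tests will be conducted against a two-sided alternative hypothesis, employing a significance level of 0.05". The hierarchy in that section lists only the primary and the four secondary efficacy endpoints.

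**The concern.** A chi-square or Fisher test on an r x 2 table treats the pain levels, or the counts 0, 1, 2 and so on, as unordered labels. Shuffle the labels and the p-value stays the same. With r categories the chi-square spreads its power over r - 1 degrees of freedom, while the clinical question has one direction: do children in one arm hurt more, need more donor sites, or come back more often?

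The SAP does use numeric order elsewhere. LEFS, QuickDASH and POSAS scores and days of antibiotic exposure are compared by one-way ANOVA. It gives no reason for treating these three outcomes differently.

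Pain by FPS-R and rates of hospital readmission are named safety outcomes in the protocol synopsis and in SAP 7.2.3.6. At stake is the sensitivity of those comparisons: a real shift may be missed and its non-significant result read as reassurance, or a patternless difference may be flagged.

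**Working it through.** The documents state no power for these outcomes, so there is no figure to reproduce. As a check on method, exact Fisher power for surgical excision (SAP 9.1.2: 0.44 v 0.78, 80 per arm) came out at 99.2%, against 99.1% stated.

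**Inputs from the documents.** Two-sided 5% level (SAP 11.1.9). 145 patients, about 72 per arm at 1:1 (SAP 13.3 and 11.1.11). The two older age groups hold 50 + 20 = 70 children, so about 35 per arm. The two younger groups hold 45 + 30 = 75.

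**Assumed, not in the documents.** Six FPS-R levels, all category distributions, the numbers of count categories, a proportional-odds shift for the ordered categories, and negative binomial counts in step 4.

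**Step 1: theory.** Suppose a 1-df ordered test has a given power. Its noncentrality is λ = (1.96 + z)², where z is the normal quantile of that power; for 80%, (1.96 + 0.842)² = 7.85. Give the same λ to a chi-square test with r - 1 df:

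| Ordered test | λ | 3 categories | 4 | 5 | 6 |
|---|---|---|---|---|---|
| 50% | 3.84 | 40% | 35% | 31% | 28% |
| 80% | 7.85 | 71% | 65% | 60% | 56% |
| 90% | 10.51 | 84% | 78% | 74% | 70% |

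To get back to 80%, the unordered test needs 1.23, 1.39, 1.52 or 1.63 times the sample size for 3, 4, 5 or 6 categories.

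**Step 2: pain, simulated.** 35 per arm, assumed control distribution .30/.25/.20/.12/.08/.05, Pearson chi-square against tie-corrected Wilcoxon:

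| Common odds ratio | Chi-square | Wilcoxon | Loss (points) |
|---|---|---|---|
| 2.5 | 30% | 57% | 27 |
| 3 | 44% | 73% | 29 |
| 4 | 67% | 89% | 22 |

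The Fisher fallback could well apply here. At odds ratio 2.5, the cumulative odds below the top level fall from .95/.05 = 19 to 19/2.5 = 7.6, so the top level has probability 1/8.6 = .116. Its expected count per arm is 35 × (.05 + .116)/2 = 2.9. Simulated Fisher power is 31% at odds ratio 2.5 and 46% at 3, in effect the same as chi-square.

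**Step 3: donor sites, simulated.** With 4 to 5 assumed categories and Wilcoxon at 80%, chi-square has 56% to 64%, a loss of 16 to 24 points.

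**Step 4: readmission counts, simulated.** With 3 to 4 assumed categories and Wilcoxon at about 80%, chi-square has 62% to 69%. In the sparsest case (85% with no readmission, 36 per arm) it was 51% against 76%.

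With negative binomial counts, 72 per arm and means 0.5 v 1.1, the result depends strongly on the dispersion k (variance = mean + mean²/k): 43% v 78% at k = 1, 80% v 94% at k = 5. At k = 1 Fisher's test has 52%, about 25 points below Wilcoxon.

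When events are sparse (means 0.1 v 0.35, k = 1), the yes/no test has 77% and Wilcoxon 79%; the r x 2 chi-square has 59%.

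**The case against.** **Readmission is already covered.** The protocol outcome is the rate of readmission, which SAP 10.3.4.4 defines first as a patient-level yes/no variable and 11.1.5.13 tests as a proportion. Order is irrelevant there, and step 4 shows little loss when most patients have zero or one event. This stands for overall readmission, which is why the readmission counts are only a lesser point. It does not reach planned and unplanned readmissions taken separately, since the per-patient proportion test is specified for any readmission.

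**The SAP switches to Fisher on sparse tables.** True, so a criticism of the type I error of Pearson's test on sparse counts would miss the planned procedure. The power loss remains, because Fisher ignores order too.

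**Readers will see a shift anyway.** Numeric summaries, changes from baseline, shift tables and target-wound pain adverse events are all reported, donor-site area has its own ANOVA, and the protocol judges safety mainly on adverse event frequency. This limits the damage, but still leaves no between-group test of the pain score or donor-site count that uses order.

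**A stronger reading: about half the power is lost.** A reader might infer this from the low-power cases. For six-level pain, an ordered test at 50% corresponds to roughly 25% to 28% for chi-square. With the ordered test at 80%, the relative loss is 31% to 36% for pain, 20% to 30% for donor sites and 13% to 24% for readmission counts outside the sparsest case. About half is not a general figure.

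**Conclusion.** The point holds for FPS-R and the number of donor sites, and as a lesser point for the numbers of planned and unplanned readmissions. Each is ordered, and its only planned between-group test ignores order. Against a one-directional shift the loss is roughly 10 to 30 percentage points, most for six-level pain in the older children. A single Pearson setting with highly dispersed counts goes to 35 points, but the planned Fisher fallback would bring that to about 25. These sizes rest on the assumed distributions, number of levels and form of shift; the direction of the loss does not depend on those particular values.

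A reader might also infer that the trial's efficacy conclusions are weakened. The documents do not support that: pain and readmissions are safety outcomes, donor sites are exploratory, all lie outside the hierarchy, and no power is claimed for them. The consequence is limited to sensitivity: a non-significant result from these tests should not be read as showing no difference.

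**What to change.** - **FPS-R (11.1.5.7):** replace the chi-square/Fisher comparison with a Wilcoxon rank-sum or CMH row-mean-scores test, run separately above and below age 4 as the section already requires. Stratify by age group only within each range; stratifying across all ages would combine scores from the range where the scale is validated with scores from the range where it is not.
- **Donor-site number (11.1.6.4) and numbers of planned and unplanned readmissions (11.1.5.13):** replace it with a Wilcoxon test or a negative binomial comparison.
- **All of these:** report an effect estimate with a 95% CI, and keep the frequency tables and the yes/no readmission test.

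The cost is SAP wording and some reprogramming with standard procedures. It needs no new data and leaves the hierarchy and sample size unchanged.

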11.1.5.8. Blood Transfusions

The volume of blood transfusions in milliliters (as calculated in Section 10.3.4.4) will be presented by treatment group using descriptive statistics. The mean volume of blood transfusions between treatment groups will be compared by a one-way analysis of variance.

The volume of blood transfusions will be presented overall (during hospitalization), as well as separately for volumes transfused before start of treatment, during the ER period, within 1 week after the ER period and later than 1 week after the ER period.

The volume of blood transfusions will be analyzed as described above separately for calculated transfusion RBC volume, for the volume of packed red blood cells transfused and the volume of whole blood transfused.

11.1.5.9. Immunogenicity and PK Evaluation

The immunogenicity and PK evaluation will be done separately and is described in a separate document.

11.1.5.10. Antibiotic Use

The number of days of exposure to systemic antibiotic drugs will be presented by treatment group using descriptive statistics and compared between groups with a one-way analysis of variance. This analysis will be conducted for overall systemic antibiotic use, for antibiotic use due to AE involvement (as indicated in the eCRF) and for prophylactic antibiotic use (as indicated in the eCRF) separately.

11.1.5.11. Medical History

Medical history events will be classified using the MedDRA dictionary. They will be tabulated with reference to system organ class, preferred term and frequency of occurrence. The system organ classes will be sorted alphabetically, the preferred terms within the system organ classes will be displayed in decreasing order of incidence in the NexoBrid group.

11.1.5.12. Concomitant Medications

In this analysis, only the concomitant medications administered during the first phase (until the 12 months follow-up for each patient) will be analyzed. The number of patients involved will be tabulated with overall numbers and with reference to ATC coding using the Level 2 and Level 4 codes. The summary tables will be produced separately for the following sub-periods: 1) until the 12 weeks follow-up, 2) between the 12 weeks follow-up and the 12 months follow-up (including CM with a start date before the 12 weeks follow up but an end date after that or still ongoing), 3) combined until the 12 months follow-up.

11.1.5.13. Hospital Readmission Rates

Hospital admission rates will be analyzed on a patient level by displaying counts and percentages by treatment group. The proportion of patients needing readmission to a hospital will be compared between treatment groups using a chi square test (or Fisher's exact test in case of small estimated cell counts).

Furthermore, the number of planned hospital readmissions per patient will be analyzed by displaying counts and percentages by treatment group. The number of planned hospital readmissions per patient will be compared between treatment groups using a chi square test (or Fisher's exact test in case of small estimated cell counts).

Additionally, the number of unplanned hospital readmissions per patient will be analyzed by displaying counts and percentages by treatment group. The number of unplanned hospital readmissions per patient will be compared between treatment groups using a chi square test (or Fisher's exact test in case of small estimated cell counts).

Hospital readmission will also be analyzed on a readmission level. Counts and percentages of planned/unplanned readmissions will be displayed by treatment group. The proportion of planned/unplanned readmissions to hospitals will be compared between treatment groups using a chi square test (or Fisher's exact test in case of small estimated cell counts).

11.1.5.14. Change in PTT/INR

Change in INR/PTT will be evaluated at 4h post first treatment. For the classification of normal and abnormal INR/PTT values, the reference limits of the local labs will be used (see also Section 10.3.4.4).

The following tables will be produced for INR and PTT:

- Shift tables indicating shifts from baseline (low/normal/high) to post first treatment (low/normal/high) as well as a listing of subjects experiencing shifts from low/normal to high
- Shift tables indicating shifts from baseline to post first treatment potentially clinically significant result as well as a listing of subjects experiencing such shifts. For the definition of pCS high and pCS low, see Section 13.2.2.

Only subjects with non-missing pre and post values will be considered for the analysis.

